5.2.2.1 Infections

If a patient develops a clinically significant infection of any grade, initiation of treatment cycles will be delayed or withheld until the infection is clinically controlled (e.g., the patient is afebrile and with improving signs/symptoms). Treatment (i.e., subsequent cycles) may then resume at the full dose. At the discretion of the investigator, prophylactic therapy to prevent recurrence of infection can be instituted as clinically indicated.

5.2.2.2 Non-infectious, drug-related

a) First or second occurrence of a drug-related \geq grade 3 toxicity:

If toxicity recovers to Grade 1 within 35 days from the onset of the toxicity: study therapy is to be restarted at 25% reduction with no alteration in schedule from the previous doses for all subsequent cycles.*

If toxicity **does not** recover to Grade 1 within 35 days from the onset of toxicity: the patient should not receive additional study drug.*

* Excludes NCI CTC grade 2 alopecia and \geq grade 3 anorexia, transient elevations in hepatic transaminases or alkaline phosphatase based on institutional normals without clinical significance, and nausea/vomiting, diarrhea or mucositis that resolves (with or without supportive care) to < grade 2 within 72 hours of onset to grade 3.

b) 3rd Occurrence of a drug-related non-infectious event(s): Grade 3 toxicity:

The patient should not receive any additional treatment.

5.3 Supportive Care

5.3.1 Blood Products

All blood products are to be irradiated and leukocyte-reduced according to institutional guidelines.

5.3.2 Infection Prophylaxis

The use of prophylactic antibacterial, antifungals, and antiviral agents is recommended according to standard of care.

5.3.3 Colony Stimulating Factors

Hematopoietic growth factors (e.g., granulocyte colony stimulating factor [G-CSF]) can be administered at the treating physician's discretion and judgment.

5.3.4 Concomitant Therapy

No systemic concomitant cytotoxic therapy or investigational therapy is allowed during the study.

To the extent possible, use of nephrotoxic (e.g., vancomycin, amphotericin B, etc) and hepatotoxic (e.g., voriconazole, cyclosporine, etc) agents is strongly discouraged and is to be avoided during clofarabine administration for all treatment cycles unless there are compelling reasons to do so.

6.0 Pretreatment evaluation

History and physical.

CBC with differential and platelets, chemistry profile (total bilirubin, serum creatinine, SGPT or SGOT, uric acid, LDH, potassium, magnesium) within 14 days of therapy start.

Bone marrow aspirate and/or biopsy within 28 days of therapy start. The bone marrow evaluation must include cytogenetic studies except for situations where cytogenetic analysis was not added to a bone marrow aspirate and/or biopsy and the stage/prognostic group of the MDS can be ascertained as higher risk based on the available information (eg, blasts and/or degree of cytopenias).

Pregnancy (urine or blood) test for women of childbearing potential within two weeks of start of therapy. Child bearing potential is defined as not post-menopausal for 12 months or no previous surgical sterilization.

7.0 Evaluation During Study

CBC with differential and platelet counts at least weekly while on therapy and every 4 to 8 weeks thereafter as long as on study. No differential is needed if the WBC is $< 1.0 \times 10^9/L$.

Chemistry profile (at least creatinine, SGOT or SGPT, total bilirubin, potassium, magnesium) every two weeks while on therapy, then every 4 to 8 weeks as long as on study.

Bone marrow aspirate and/or biopsy at the end of course 1 (day 28 +/- 7 days). If a patient is not in remission at this point, further bone marrow aspirate and/or biopsy can be scheduled as per the investigator's discretion and mandated by the development of the peripheral blood counts.

No repeat bone marrow is necessary if non-response or progressive disease can be unequivocally diagnosed from peripheral blood tests, or, in patients with a WBC \leq 0.3 if the bone marrow test is considered non-contributory by the investigator at any time point.

Follow up marrow tests should include cytogenetic analysis for those patients who had abnormalities prior to therapy start.

Repeat physical examination (problem focused) prior to administration of each course

After completion of therapy and as long as still on study, patients will return to MD Anderson Cancer Center for repeat physical examination (problem focused), repeat CBC with differential and platelet count, and chemistry profile (at least creatinine, SGOT or SGPT, total bilirubin, potassium, magnesium) every 6 months (+/- 2 months). A CBC with differential and platelet count should be checked every one to two months, but these blood tests may be done locally.

8.0 Criteria for Response

Category	Response Criteria (responses must last for at least 4 weeks)
Complete remission (CR)	Marrow: \leq 5% myeloblasts with normal maturation of all cell lines. Persistent dysplasia will be noted (dysplastic changes should consider the normal range of dysplastic changes.) Blood: - Hemoglobin (Hb) \geq 11 g/dL (untransfused, patient not on EPO) - Neutrophils \geq $1 \times 10^9/L$ (not on myeloid growth factor) - Platelets \geq $100 \times 10^9/L$ (not on thrombopoietic agent) - No blasts
Partial remission (PR)	All CR criteria (if abnormal prior to treatment), except: Marrow blasts decreased by \geq 50% compared with pretreatment but still $>$ 5%. Cellularity and morphology not relevant
Marrow CR	Marrow: \leq 5% myeloblasts and decrease by \geq 50% over pretreatment Blood: if hematologic improvement (HI) responses, they will be noted in addition to the marrow CR
Stable disease (SD)	Failure to achieve at least PR, but no evidence of progression for $>$ 8 weeks.
Failure	Death during treatment or disease progression characterized by worsening of cytopenias, increase in percentage of marrow blasts, or progression to an MDS FAB subtype more advanced than pretreatment.
Relapse after CR or PR	At least one of the following: - Return to pretreatment bone marrow blast percentage - Decrement of \geq 50% from maximum remission/response levels in granulocytes or platelets - Reduction in Hb concentration by \geq 1.5 g/dL or transfusion dependence (in the absence of another explanation, such as acute infection, GI bleeding, hemolysis, etc.)
Cytogenetic response	Complete: Disappearance of the chromosomal abnormality without appearance of new ones Partial: At least 50% reduction of the chromosomal abnormality

Disease progression	
For patients with
 
< 5% blasts: $\geq 50\%$ increase in blasts to > 5% blasts 5%-10% blasts: $\geq 50\%$ increase in blasts to > 10% blasts 10%-20% blasts: $\geq 50\%$ increase in blasts to > 20% blasts 20%-30% blasts: $\geq 50\%$ increase in blasts to > 30% blasts
 
Any of the following: At least 50% decrement from maximum remission/response levels in granulocytes or platelets. Reduction in Hb concentration by ≥ 2 g/dL. Transfusion dependence (in the absence of another explanation, such as acute infection, GI bleeding, hemolysis, etc.)

Hematologic Improvement	Response Criteria (responses must last at least 8 weeks)
Erythroid response (pretreatment, < 11 g/dL)	
Hb increase by ≥ 1 g/dL Relevant reduction of units of RBC transfusions by an absolute number of at least 4 RBC transfusions/8wk compared with the pretreatment transfusion number in the previous 8 wk. Only RBC transfusions given for a Hb of ≤ 9 g/dL pretreatment will count in the RBC transfusion response evaluation

Platelet response (pretreatment, < 100x10 ⁹ /L)	
Absolute increase of $\geq 30 \times 10^9/L$ for patients starting with > 20 x 10⁹/L Increase from < 20 x 10⁹/L to > 20 x 10⁹/L and by at least 100%

Neutrophil response (pretreatment, < 1 x 10 ⁹ /L)	At least 100% increase and an absolute increase > 0.5 x 10 ⁹ /L
Progression or relapse after HI	
At least 1 of the following:
 
At least 50% decrement from maximum response levels in granulocyte or platelets Reduction in Hb by ≥ 1.5 g/dL Transfusion dependence (in the absence of another explanation, such as acute infection, GI bleeding, hemolysis, etc.)

Reference: Cheson et al. 2006

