4.0 Patient Eligibility

Inclusion:

- 1) Age \geq 18 years.
- 2) Diagnosis of MDS confirmed within 10 weeks prior to study entry according to WHO or FAB criteria. Patients are either not eligible for or choose not to proceed with a stem cell transplant.
- 3) MDS classified as follows: RAEB-1 (5%-9% BM blasts); RAEB-2 (10%-19% BM Blasts); CMML (5%-19% BM blasts); RAEB-t (20%-29% BM blasts) AND/OR by IPSS: intermediate-2 and high risk patients.
- 4) No response, progression, or relapse (according to 2006 IWG criteria; see section 8 for details) following at least 4 cycles of either azacitidine or decitabine, or following at least 2 cycles of SGI-110, which were completed within the last 2 years - AND/OR - intolerance to azacitidine, decitabine, or SGI-110 defined as drug-related \geq grade 3 hepatic or renal toxicity leading to treatment discontinuation during the preceding 2 years.
- 5) Eastern Cooperative Oncology Group (ECOG) performance status of \leq 2.
- 6) Willing to adhere to and comply with all prohibitions and restrictions specified in the protocol.
- 7) Patient (or patient's legally authorized representative) must have signed an informed consent document indicating that the patient understands the purpose of and procedures required for the study and is willing to participate in the study.

Exclusion:

- 1) Uncontrolled intercurrent illness including, but not limited to, symptomatic congestive heart failure, unstable angina pectoris, or cardiac arrhythmia.
- 2) Active infection not adequately responding to appropriate antibiotics (i.e. ongoing temperatures of \geq 38 degree Celsius).
- 3) Total bilirubin \geq 1.5 mg/dL and not related to hemolysis or Gilbert's disease. Patients with total bilirubin \geq 1.5 mg/dL to 3 mg/dL are eligible if at least 75% of the bilirubin is indirect.
- 4) Alanine transaminase (ALT/SGPT) or aspartate transaminase (AST/SGOT) \geq 2.5 x the upper limit of normal.
- 5) Serum creatinine $>$ 1.5 mg/dL.
- 6) Female patients who are pregnant or lactating.
- 7) Patients with reproductive potential who are unwilling to following contraception requirements (including condom use for males with sexual partners, and for females: prescription oral contraceptives [birth control pills], contraceptive injections, intrauterine devices [IUD], double-barrier method [spermicidal jelly or foam with condoms or diaphragm], contraceptive patch, or surgical sterilization) throughout the study.

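### CR has no condition relative to pretreatment although patients may enter with blasts already within the CR limit, and the marrow relapse criterion misfires for the same patients

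*Combined protocol and SAP*

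**What the plan says.** Inclusion criterion 3 (Section 4.0) offers two routes. The blast route lists "RAEB-1 (5%-9% BM blasts); RAEB-2 (10%-19% BM Blasts); CMML (5%-19% BM blasts", and then RAEB-t. The second route is "AND/OR by IPSS: intermediate-2 and high risk patients", with no blast minimum attached. No inclusion criterion asks for a cytopenia. Inclusion criterion 4 also admits patients who stopped a hypomethylating agent for drug-related hepatic or renal toxicity, without requiring that the drug had failed.

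Section 8.0 defines CR by a marrow with at most "5% myeloblasts with normal maturation of all cell lines", together with:
- hemoglobin of at least 11 g/dL, untransfused and off EPO;
- neutrophils of at least 1 x 10^9/L, off growth factor;
- platelets of at least 100 x 10^9/L, off thrombopoietic agents;
- no blood blasts.

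Responses must last at least 4 weeks. Persisting dysplasia is recorded, but the row does not say whether it rules out CR.

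Marrow CR, by contrast, asks for at most "5% myeloblasts and decrease by" at least 50% from pretreatment. Relapse after CR or PR is scored on any one of several items, the first being "Return to pretreatment bone marrow blast percentage".

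CR is a primary objective (Sections 1.0 and 10.0) and drives the futility rule in Table 1a. Duration of response and relapse-free survival are secondary objectives.

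**The concern.** The CR blast limit and the entry range share the value 5%, and by the IPSS route everything below it. CR is scored on absolute thresholds alone. The plan therefore has no rule for a patient whose pretreatment marrow and blood already satisfy them, and such a patient could be credited to clofarabine plus cytarabine as a response.

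The relapse item assumes that the pretreatment blast percentage lies above the CR limit. For a patient who entered at or below 5% it does not, so relapse can be scored on a marrow that still qualifies as CR.

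At stake are the CR count used for futility and for the final estimate, and the end dates of response and relapse-free survival.

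**Working it through.** **Step 1. Where entry and the CR blast limit overlap.**

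| Entry route (Section 4.0) | Pretreatment blasts | CR limit of 5% or less already met? |
|---|---|---|
| RAEB-1, "RAEB-1 (5%-9% BM blasts" | exactly 5% | yes |
| RAEB-1 | above 5%, to 9% | no |
| CMML, "CMML (5%-19% BM blasts" | exactly 5% | yes |
| CMML | above 5%, to 19% | no |
| RAEB-2, RAEB-t | 10% or more | no |
| IPSS intermediate-2 or high | no minimum stated | yes, if 5% or less |

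**Step 2. Which response categories refer to pretreatment (Section 8.0).**
- PR: blasts down by at least 50%; the CR items apply where they were abnormal before treatment.
- Marrow CR: blasts down by at least 50%.
- Cytogenetic response: loss or reduction of an existing abnormality.
- Hematologic improvement: each row requires a pretreatment deficit (Hb below 11 g/dL, platelets below 100, neutrophils below 1 x 10^9/L).
- CR: none.

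**Step 3. What a CR with no change would require.** At entry the patient needs all of these: blasts of 5% or less; maturation read as normal; Hb, neutrophils and platelets within the limits without transfusion or growth factors; and no blood blasts. The state must then persist for 4 weeks. A patient who fails any one of these at entry has to improve to become a CR. Nothing in Section 4.0 excludes a patient who meets all of them, and no figure in the documents says how many there are.

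**Step 4. The relapse item.** This does not need normal counts at entry.
- A patient enters at 3%, dips lower, recovers counts and is in CR. A later marrow at 3% is back at the pretreatment percentage, so one relapse item is met although 3% is within the CR limit.
- A patient enters at 5%, recovers counts and stays at 5%. Whether an unchanged value counts as a return is open to interpretation.
- For a patient entering at 10% or more, a return to pretreatment lies outside the CR limit, and the conflict does not arise.

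The effect is to date relapse too early in low-blast entrants, which shortens their duration of response and relapse-free survival.

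**Step 5. Illustration on the futility rule.** Inputs from Section 10.0: prior beta(0.4, 1.6); stop if Pr(CR rate > 0.20) < 0.01; boundaries in Table 1a; maximum 80 patients.

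The posterior after x CRs in n patients is beta(0.4 + x, 1.6 + n - x). For x = 1, Pr(rate > 0.20) is 0.0116 at n = 23 and 0.0094 at n = 24, which matches the printed 1/24. All boundaries from 1/24 to 8/78 reproduce. With zero CRs the rule is first met at n = 13 and the table starts at 15; the printed table is used here. An exact patient-by-patient recursion gives stop probabilities of 0.991, 0.739, 0.303 and 0.086 at true rates 0.05, 0.10, 0.15 and 0.20. Table 1b prints 0.992, 0.735, 0.301 and 0.086.

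Let f be the share of patients already in CR at entry (assumed, 0 to 10%) and p the true CR rate in the others. The apparent rate is f + (1 - f)p; for example 0.025 + 0.975 x 0.10 = 0.1225.

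| f | Patients of 80 | Apparent rate, p = 0.10 | Stop probability, p = 0.10 | Stop probability, p = 0.05 |
|---|---|---|---|---|
| 0 | 0 | 0.100 | 0.739 | 0.991 |
| 2.5% | 2 | 0.1225 | 0.529 | 0.925 |
| 5% | 4 | 0.145 | 0.338 | 0.761 |
| 10% | 8 | 0.190 | 0.112 | 0.338 |

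Two statements need no assumed share. Each such patient adds 1/80 = 1.25 points to the CR rate at full enrolment. One such patient among the first 15 removes the 0/15 stop.

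**The case against.** A reader might infer that any entrant with 5% or fewer blasts already meets the marrow part of CR, and so can be scored CR unchanged. The documents do not support that. The marrow part also requires normal maturation of all cell lines, and CR further requires every unsupported blood limit and 4 weeks' duration. By the blast route the overlap is a single value, exactly 5%.

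The IPSS route is wider but may work against the count limits. The scoring table is not in the documents, and Section 6.0 says that a patient "can be ascertained as higher risk based on the available information (eg, blasts and/or degree of cytopenias", so a low-blast entrant may qualify partly through cytopenias. The toxicity-intolerance route still requires inclusion criteria 2 and 3. Sections 2.0 and 5.1.1 describe patients whose treatment has failed and whose low counts are attributed to disease. All of this stands: the group that could be CR without change is narrow, and its existence is not shown.

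A reader might also infer that the futility rule is materially weakened. That rests wholly on the assumed share; near zero there is no effect.

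On relapse, a fair reply is that a value which never left baseline has not returned to it, so CR and relapse on the same day is a strained reading. That reply answers the patient who stays at 5%, but not the one who dips and comes back to a value still within the CR limit.

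Finally, it is tempting to require a 50% blast fall for every CR. That would depart from the response criteria the plan cites. A patient going from 9% to 5% (a fall of 4/9 = 44%) with full count recovery would be neither CR, PR (which needs more than 5%) nor Marrow CR (which needs a 50% fall), and would drop to stable disease. The overlap does not justify this.

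**Conclusion.** The point holds in two limited parts.

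First, CR is the one positive response category not anchored to pretreatment, and entry overlaps its blast limit, so the plan lacks a rule for a patient who meets every CR element at entry. That group is probably small and of unknown size. The stop probabilities of 0.53 and 0.34 against 0.74 at a true CR rate of 10% illustrate assumed shares of 2.5% and 5%; they are not estimates.

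Second, for any patient entering at 5% or below who reaches CR through count recovery, marrow relapse can be scored within the CR limit. This follows from the text without assuming normal counts at entry, and it affects both response-based secondary endpoints. The number of such patients is not given either.

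The documents do not support saying that low-blast entrants are in CR at entry, or that duration of response and relapse-free survival are undefined for all of them. The correction is cheap and should be made.

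**What to change.** Amend Section 8.0, for endpoint scoring only:

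1. A patient who meets all CR criteria on the pretreatment marrow and CBC is not counted as a CR, either in Table 1a monitoring or in the final CR rate. The patient stays in the denominator.
2. For patients entering with 5% or fewer blasts, CR requires at least one CR criterion that was unmet at baseline to become met. This puts the first rule positively and makes clear that count recovery with an unchanged marrow can still be a CR. It remains a threshold rule: Hb moving from 10.9 to 11.0 g/dL would satisfy it.
3. For those same patients, replace the return-to-pretreatment item with a rise in marrow blasts above 5%. The other relapse items stay.

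No blast-fall condition is added for other patients, and Tables 1a and 1b need no change.

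Cost: a wording change. Section 6.0 already requires a pretreatment marrow and CBC. Section 6.0 does not list transfusion or growth-factor use, which should be recorded at baseline so that the first rule can be applied; pretreatment transfusions are already needed for the erythroid response. The reported CR rate may be slightly lower.

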5.1.1 Induction

Clofarabine 10 mg/m² as a 1-2 hours i.v. infusion. daily for 5 days (days 1-5)

Cytarabine 20 mg s.c. twice daily for 7 days (days 1-7)

Cytarabine should be administered 3 to 6 hours following the start of the clofarabine infusions.

Cycles are repeated every 4 to 8 weeks depending on resolution of toxicities. No dose reductions, delays, or modifications are required for hematologic toxicities during the induction cycles. It is assumed that low counts at diagnosis are due to involvement by the disease process and require therapy for improvement. Patients who receive repeated induction cycles have persistent disease and thus no recovery of hematologic parameters can be expected.

Patients can receive up to a maximum of 3 induction cycles as long as they have stable disease and do not progress. If patients have not achieved at least a hematologic improvement after three cycles, they should be taken off study. Patients with at least hematologic improvement can continue the consolidation. Patients with any response less than CR or CRp before completion of three induction cycles can complete all three induction cycles in an effort to maximize their response prior to moving on with the consolidation if this is considered in the best interest of a particular patient.

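### An erythroid improvement of 1.0 to below 1.5 g/dL can be given back in full without meeting the hemoglobin rule for loss of response

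*Combined protocol and SAP*

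**What the plan says.** The hematologic improvement part of the table in Section 8.0 applies the erythroid row to patients with pretreatment hemoglobin below 11 g/dL. It lists "Hb increase by ≥ 1 g/dL" and a reduction of at least 4 red-cell transfusions per 8 weeks. The heading of that part requires duration: "Response Criteria (responses must last at least 8 weeks".

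Loss of HI has its own row, and any one of three findings is enough. For the white-cell and platelet lines the finding is "At least 50% decrement from maximum response levels in granulocyte or platelets". For the red-cell line there is a hemoglobin finding, given as "Reduction in Hb by ≥ 1.5 g/dL" without a reference level. The third finding is a need for regular transfusion that nothing else explains.

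The general disease progression row of the same table has a separate hemoglobin criterion, "Reduction in Hb concentration by ≥ 2 g/dL".

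HI is used in Section 5.1.1: "If patients have not achieved at least a hematologic improvement after three cycles, they should be taken off study". Inclusion criterion 4 in Section 4.0 sends the reader to Section 8.0 to judge non-response, progression or relapse after the prior hypomethylating agent. Duration of response is a secondary objective in Sections 1.0 and 10.0.

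**The concern.** A rule for losing a response should at least recognise that the patient is back where treatment began. Here the fall needed for loss is 0.5 g/dL larger than the smallest rise that counts as gain, so some responders must drop below their pretreatment hemoglobin before the hemoglobin criterion can be met.

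Two uses are exposed. The first is any reported duration of HI, which would run on after the benefit has gone. The second is eligibility. A patient whose small erythroid response to azacitidine, decitabine or SGI-110 was wholly lost is not a non-responder and, on hemoglobin, has not relapsed. Unless another criterion applies, inclusion criterion 4 gives no clear answer for that patient.

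**Working it through.** The plan states no figure that depends on this point, so there is none to reproduce. The check compares the two thresholds directly.

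**Inputs (all Section 8.0).** Gain threshold 1.0 g/dL; hemoglobin loss threshold after HI 1.5 g/dL; hemoglobin threshold for general progression 2 g/dL; minimum HI duration 8 weeks.

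**Reading used.** The hemoglobin loss line names no reference level. The granulocyte and platelet line names the maximum response level, so the hemoglobin fall is read the same way, from best response.

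**Formula.** Let g be the peak gain, held for at least 8 weeks. HI is gained if g ≥ 1.0. A full return to pretreatment is a fall of g, so it meets the loss rule only if g ≥ 1.5. The loss rule is first met at a level of g − 1.5 relative to pretreatment.

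| Peak gain g (g/dL) | HI gained | Full return scored as loss on hemoglobin | Level at which the loss rule is met, relative to pretreatment |
|---|---|---|---|
| 0.9 | no | not applicable | not applicable |
| 1.0 | yes | no | −0.5 |
| 1.2 | yes | no | −0.3 |
| 1.4 | yes | no | −0.1 |
| 1.49 | yes | no | −0.01 |
| 1.5 | yes | yes | 0.0 |
| 2.0 | yes | yes | +0.5 |
| 2.5 | yes | yes | +1.0 |

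The affected range is 1.0 ≤ g < 1.5.

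**Example.** Hemoglobin goes from 8.0 to 9.0, which is a response. A return to 8.0 is a fall of 1.0, and a further drop to 7.6 is a fall of 9.0 − 7.6 = 1.4; neither is a loss. The rule is met only at 9.0 − 1.5 = 7.5.

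**Does another rule close the gap?** The general progression row needs a 2 g/dL fall, which in the example means 9.0 − 2 = 7.0, so it comes later still. The failure row mentions worsening cytopenias but gives no hemoglobin figure. The row for relapse after CR or PR does not govern HI. Nothing in the documents ends HI on return to pretreatment hemoglobin.

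**Sensitivity to the reading.** If the 1.5 g/dL were counted from pretreatment instead, the same patient would have to reach 8.0 − 1.5 = 6.5, and gains of every size would be affected. The reading used here is the more favorable one to the plan.

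**Does a common threshold close it?** If gain and loss share one value T, any qualifying gain satisfies g ≥ T, so a full return is a fall of at least T and is scored. This holds at T = 1.0 and at T = 1.5 alike.

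**The case against.** Different thresholds for gain and loss are not in themselves an error. A wider margin for loss can be deliberate, so that ordinary fluctuation is not scored as relapse. That is fair, but Section 8.0 gives no such reason, and a margin that lets a patient sit below the starting value while still in response goes beyond damping noise.

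Hemoglobin is also only one of three routes to loss. A patient at 7.6 g/dL may well become transfusion dependent, or may be judged a failure for worsening cytopenias. This stands and narrows the effect, but neither route is tied to giving back the gain.

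A reader might infer more than the documents support:
- *That anyone who gives back the gain stays a responder.* This is not so for gains of 1.5 g/dL or more. A gain given back before 8 weeks was never HI.
- *That the secondary endpoint is biased.* This would need duration of response to include HI, which the documents do not say.
- *That the mismatch decides who goes on to consolidation.* The rule in Section 5.1.1 turns on achieving HI, hence on the gain threshold alone.
- *That 1 g/dL turns random variation into response.* The documents give no within-patient hemoglobin variability and do not say how lasting 8 weeks is scored, so no rate of false response can be derived from them.
- *That 1 g/dL is a slip for 1.5.* The cited 2006 criteria are not reproduced, so the documents cannot settle which figure was meant.

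**Conclusion.** The mismatch is real and follows from the plan's own figures: for peak gains of 1.0 to below 1.5 g/dL, the hemoglobin criterion leaves a patient in HI after full return to pretreatment, and down to as much as 0.5 g/dL below it. This assumes that the fall is measured from best response, that the gain first lasted 8 weeks, and that no other loss criterion is met.

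The consequences are limited. HI duration is overstated for these patients, and some lost responses to a prior agent may not be scored as relapse under inclusion criterion 4. The documents give no distribution of hemoglobin gains, so the number of patients affected cannot be estimated. HI enters neither primary endpoint (CR, overall survival) nor any stopping rule. This is a correction to consider, not one on which the trial's main conclusions depend.

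**What to change.** Reconcile the gain and loss lines for erythroid HI in Section 8.0 with each other and with the 2006 criteria that the table cites. State the level from which the hemoglobin reduction is measured, and make sure that a return to pretreatment hemoglobin counts as loss of erythroid HI; a common threshold or an explicit return-to-pretreatment rule would each achieve this. Apply the reconciled definition in inclusion criterion 4. No value is proposed here: HI also decides who remains on study after induction, and the documents do not show which figure was intended.

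The cost is about one line in Section 8.0. The reported HI rate or HI duration may become slightly less favorable.
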